Study Protocol and Statistical Analysis Plan

Investigating Hearing Aid Frequency Response Curves - ID# 12792

July 24, 2024

NCT05828017

Investigating Hearing Aid Frequency Response Curves - ID# 12792

1 Objectives and hypotheses of the clinical investigation

1.1 Purpose of the clinical investigation claims for clinical performance, effectiveness or safety of the investigational device that are to be verified

This exploratory study evaluates a series of proposed frequency gain curves, comparing them to our current frequency gain curve across various hearing aid programs and configurations (both acoustic and streaming). Participants were asked to rate speech clarity, noise intrusion, comfort, and overall preference in the presence of live stimuli. Additionally, they were asked to rank two proposed streaming frequency response curves alongside our current standard streaming curve. SRT50 scores were also collected using the US Matrix test task. The aim of this clinical investigation is to assess whether the proposed gain offsets provide benefits for hearing aid users in different listening environments.

1.2 Primary Objective

The primary objective of this study was to evaluate whether participants with moderate to severe sensorineural hearing loss (SNHL) prefer a newly proposed frequency gain curve (Variation #1) compared to our current frequency response curve, when fitted with different hearing aid programs or under various hearing aid settings. Testing was conducted in a controlled lab environment, where participants listened to a range of stimuli to assess which program they preferred and how they rated each program based on various sound quality metrics.

1.3 Secondary Objectives

One secondary objective of this study was to assess whether two newly proposed streaming frequency response curves (Variation #2 and Variation #3) are preferred by hearing aid users compared to our current streaming frequency response curve, across various musical genres and speech stimuli.

Another secondary objective was to evaluate the impact of the proposed frequency response curve (Variation #1) on speech performance in noise, specifically by comparing SRT50 scores to those obtained with the current frequency response curve. Participants will complete a standardized test (OLSA – US Matrix test) in noise within a sound booth, under three conditions: a program with the proposed frequency response curve, a program with the current frequency response curve, and an unaided condition (without hearing aids).

2 Design of the clinical investigation

2.1 General

2.1.1 Design Type

This clinical investigation was an interventional study conducted at two investigation sites. The study involved a single group of participants who were tested under all conditions in a crossover design. During the live preference ratings, participants were blinded to the program they were using, although the investigator was aware of the program, as they programmed the hearing aids prior to testing. For the streaming sound quality task, participants wore headphones, and both participants and investigators were blinded to the program being rated.

The table below indicates the various programs that each participant evaluated.

Programs	Interventions
Acoustic Programs	
Program 1	Standard Frequency Response Curve
Program 1	Proposed Frequency Response Curve - Variation #1
Program 2	Standard Frequency Response Curve
Program 2	Proposed Frequency Response Curve - Variation #1
Program 3	Standard Frequency Response Curve
Program 3	Proposed Frequency Response Curve - Variation #1
Program 4	Standard Frequency Response Curve
Program 4	Proposed Frequency Response Curve - Variation #1
Streaming Programs	
Program 5	Current Streaming Frequency Response Curve – Variation #2
Program 5	Proposed Streaming Frequency Response Curve - Variation #3
Program 5	Proposed Streaming Frequency Response Curve - Variation #4
US Matrix Test Task Programs	
Program 1	Standard Frequency Response Curve
Program 1	Proposed Frequency Response Curve - Variation #1
Unaided	No hearing devices

Acoustic Task:

Participants were seated in the center of a 12-loudspeaker array, positioned at azimuths of 0°, 30°, 60°, 90°, 120°, 150°, 180°, 210°, 240°, 270°, 300°, and 330° in a sound-treated room. The 12 speakers were used to render ambisonic audio scenes. While immersed in these scenes, participants were asked to toggle between two frequency response curves: the standard curve and the proposed frequency response curve – Variation #1 – using an iPhone.

Participants were then asked to rate the following attributes for each program:

1. Which program resulted in increased noise intrusion?
2. Which program provided better speech clarity?
3. Which program offered greater comfort?
4. Which program did they prefer overall?

The responses were tallied for further analysis. This process was repeated for four different hearing aid programs, where the frequency response curves were compared but not the programs themselves. In other words, ratings from one hearing aid program were not compared with those from another.

Streaming Task:

Participants were asked to wear headphones while listening to three versions of the same pre-recorded stimulus: the Current Streaming Frequency Response Curve (Variation #2), the Proposed Streaming Frequency Response Curve (Variation #3), and the Proposed Streaming Frequency Response Curve (Variation #4). This process was repeated with multiple different stimuli. After listening to each version for each stimulus, participants were asked to rank them from most preferred to least preferred, with one version ranked in between. Responses were recorded on a laptop, and the rankings for each curve were tallied and compared at the end for further analysis.

US Matrix Test Task:

Participants were seated at the center of an 8-loudspeaker array positioned at azimuths of 0°, 45°, 90°, 135°, 180°, 225°, 270°, and 315° within a sound-treated room. Noise was presented from all speakers, except the one at 0° azimuth, while speech was presented from the front speaker at 0°. Participants were asked to repeat sentences they heard while wearing hearing aids programmed with either the Standard Frequency Response Curve or the Proposed Frequency Response Curve – Variation #1, or while wearing no hearing aids at all. A total of 20 sentences were presented for each condition. At the end of the experiment, a dB SNR (signal-to-noise ratio) score was calculated for each condition and used for further analysis.

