2.1.2 Investigation-related Procedure

Recruitment paths:

- Our internal database was accessed to see if any potential participants who fit the inclusion criteria are available.
- Referrals from hearing healthcare providers in the Kitchener and surrounding area were requested.

Tasks

Appointment tasks are listed in the table below.

Tasks per appointment visit.

Visit 1	Visit 2	Visit 3

• The visit will last approximately 2 hours.• Participants will come in and will be asked to complete the following:• Study consent form and related forms will be reviewed and signed.○ Hearing test will be completed (including otoscopy, tympanometry, speech testing (SRT and WRS), and pure-tone threshold testing (air and bone))• Earmold impressions taken	
• The visit will last approximately 2 hours.• Participants will come in and will be asked to complete the following:• Earmolds are fit to participants and hearing aids are programmed• Real ear measurements taken• Live sound quality and preference ratings task is completed.	
• The visit will last approximately 2 hours.• Participants will come in and will be asked to complete the following:• US Matrix test conducted• Streaming sound quality ratings task completed• At the end of data collection, participant will be debriefed and compensated for their time.

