2.4.3 Secondary Endpoint Analysis

The secondary analysis focused on the subjective sound quality ratings provided by participants during the streaming task. Participants were asked to rank three stimuli in order of overall preference and sound quality, with each stimulus corresponding to one of the three frequency response curves being tested (Variations #2, #3, or #4). The analysis involved calculating the mean number of times each curve was ranked as the highest, lowest, and middle choice across all stimuli.

The analysis proceeded as follows:

1. **Chi-Square Analysis (First Step):** A chi-square test was conducted at each ranking level (highest, middle, and lowest) to determine how each frequency response variation was ranked.
2. **Chi-Square Analysis (Second Step):** Two additional chi-square tests were run at each ranking level to compare how the proposed frequency response curves (Variations #3 and #4) were ranked against Variation #1.

In total, 9 chi-square analyses were performed for this task.

For the speech-in-noise tests, the average SRT50 scores across all participants were compared to determine equivalence. Lower SRT50 scores indicate better performance.

1. **One-Way ANOVA:** A one-way ANOVA was conducted to assess the impact of the different interventions (standard curve, Variation #1, and unaided) on the SRT50 scores.
2. **Post-Hoc Analyses:** Post-hoc pairwise comparisons were conducted following the ANOVA, where one intervention was excluded at a time to assess differences between the remaining interventions.

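### The plan describes no randomised or balanced order for the Matrix conditions and no rule for toggle position, and no analysis adjusts for either, so the standard versus Variation #1 contrast is unprotected against order and position bias

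*Combined protocol and SAP*

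**What the plan says.** Section 2.1.1 describes the design in one sentence: "The study involved a single group of participants who were tested under all conditions in a crossover design". In the acoustic task, which carries the primary objective, "participants were asked to toggle between two frequency response curves: the standard curve and the proposed frequency response curve". The text does not say which curve occupied which toggle position, or whether that changed between participants or programs.

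Section 1.3 says the speech test is done "under three conditions: a program with the proposed frequency response curve, a program with the current frequency response curve, and an unaided condition". Section 2.1.1 adds its length: "A total of 20 sentences were presented for each condition". The visit table in section 2.1.2 places this test in Visit 3 ("US Matrix test conducted"). No order, rotation of sentence lists or practice list is mentioned.

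The related safeguard is blinding. In the live ratings "participants were blinded to the program they were using, although the investigator was aware of the program"; in the streaming task "both participants and investigators were blinded to the program being rated". No blinding is stated for the Matrix test.

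For the analysis, section 2.4.2 uses chi-square tests on tallied choices. Section 2.4.3 says of SRT50: "A one-way ANOVA was conducted to assess the impact of the different interventions". Intervention is its only factor, and neither section includes a term for order, period or position.

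**The concern.** A crossover comparison is free of order bias only if order is balanced across participants or varies and is modelled. The plan commits to neither. The two tasks are exposed differently.

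- **Matrix test (secondary).** The conditions have to be run one after another. If listeners improve with repeated sentence testing, the later condition gets a lower, better SRT50 whichever curve it is. Under a constant order, that gain is part of the estimated curve difference.
- **Acoustic task (primary).** The participant switches between the two curves, so practice hardly matters. Position does. If Variation #1 always held the same position, a habit of favouring that position would be counted as a preference for or against the curve. Blinding does not remove this, because a blinded participant still knows which position is selected.

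Standard versus Variation #1 is the contrast behind both the primary objective (section 1.2) and the speech-in-noise objective (section 1.3). The bias could favour Variation #1 or hide a benefit. The streaming task also lacks a stated playback order, but it compares other curves and lies outside this point.

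**Working it through.** **1. What the documents show about order.** They contain two listings of the Matrix conditions:

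| Place | Order listed |
|---|---|
| Section 1.3 | proposed curve, current curve, unaided |
| Section 2.1.1, program table | standard curve, Variation #1, unaided |

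The two curves are reversed between the lists, so neither can be taken as the test sequence. The actual order is unknown. The plan has no figure on this point to reproduce.

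**2. Inputs.** From the documents: 20 participants analysed (section 2.4.2). Assumed, because the documents give none: a 5% two-sided level; the size of a position habit; the practice gain; the SD of within-person SRT50 differences (1.0 to 2.0 dB). There is no true difference between the curves throughout.

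**3. Acoustic task, fixed position.** Simplify to one choice per participant with ties left out, as in the second-step chi-square test. With x of 20 choices for one curve, the statistic is (2x − 20)²/20, and the test rejects when this exceeds 3.84. That happens when x ≤ 5 or x ≥ 15. If the position holding Variation #1 is chosen with probability p, the rejection rate is P(X ≤ 5) + P(X ≥ 15) for X ~ Binomial(20, p):

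| p | Fixed position | Balanced 10/10 |
|---|---|---|
| 0.50 | 4.1% | 4.1% |
| 0.60 | 12.7% | 3.7% |
| 0.70 | 41.6% | 2.6% |

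Under balance the expected share for Variation #1 is (10p + 10(1 − p))/20 = 50% for every p.

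**4. Matrix test, fixed order.** With practice gain d and SD of differences s, a paired t-test has non-centrality d/(s/√20), 19 degrees of freedom and critical value 2.093. For d = 0.5 dB:

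| s (dB) | Non-centrality | False-positive rate |
|---|---|---|
| 1.0 | 0.5/(1.0/4.472) = 2.236 | 56.5% |
| 1.5 | 1.491 | 29.4% |
| 2.0 | 1.118 | 18.6% |

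Over the same SDs the rate is 8-19% for a 0.25 dB gain and 57-99% for 1.0 dB. When half the participants have each order, the expected bias is zero. The simulated rate of the same paired test at d = 0.5 dB is then 2.8-4.3%.

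**5. Dependence on the test.** The plan names a one-way ANOVA, not a paired test. If it was run as unpaired, differences between people enter the error term. Simulating an unpaired comparison of the two curves at d = 0.5 dB gives about 10-13% with an assumed between-person SD of 1 dB, and 0.2-2% with 2 dB. The bias in the estimated difference is still 0.5 dB. The rejection rate is low only because that test is insensitive.

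**The case against.** The strongest reply is that this is silence, not a described fault. The document is short and written largely in the past tense, so an omitted order says little about what was done. A reader might infer from the program table, which puts standard before Variation #1 in every program, that testing ran in that order. The documents do not support this: the table is introduced as an inventory of what was evaluated, and section 1.3 lists the two curves the other way round. That part of the reply stands, and the point should not be put as a finding that order was fixed.

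A second reply is that the primary task is not sequential: participants toggled freely, were blinded and could answer that the curves sounded the same. This also stands as far as it goes. It removes most of the practice argument from the primary endpoint but leaves the position argument, which needs only a constant assignment.

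A third is that the illustration rests on assumed inputs and that the paired test is not the stated analysis. Both are true. Section 2.4.3 also frames the SRT50 comparison as one of equivalence, so a false-positive difference is not the only error that matters; an order effect could equally mask a real difference. The figures show what an unprotected contrast could suffer, not what happened here.

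What remains is that a reader cannot tell from the plan whether the contrast was protected, and the stated analyses would not protect it.

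**Conclusion.** The point holds as a gap in design and analysis: no balanced order, no rule for toggle position, and no term for either. It does not establish that the results are biased.

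If order or position was constant, it coincides with the curve and no later model can separate the two. Under the stated assumptions the primary chi-square error rate would then be about three times its unbiased value at a 60% habit (12.7% against 4.1%) and about ten times at 70% (41.6%). A 0.5 dB practice gain would give 19-57% in a within-person SRT50 test, and other rates under an unpaired ANOVA. The habit, gain and SDs are all assumed, and the direction is unknown. If order and position were in fact balanced, the expected bias is zero and the remaining defect is that the plan does not say so.

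The study is exploratory and the remedy is cheap, so this is a change that should be made, not a fatal flaw.

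**What to change.** **In the plan.**
- Assign each participant to one of the six possible orders of the three Matrix conditions from a computer-generated blocked list. Twenty participants fill three blocks of six with two left over, which is near balance.
- Let software randomise, for each participant and program, which toggle position holds Variation #1, under neutral labels.
- Replace the one-way ANOVA with a within-participant SRT50 model that has condition and test position as fixed effects.

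**For sessions already completed.** Recover the actual Matrix order and toggle position from session records and state them in section 2.1.1.
- If Matrix order varied, fit the position term. If toggle position varied, report the acoustic choices by position.
- If either was fixed, its effect cannot be estimated. The corresponding standard versus Variation #1 conclusion should be reported as confounded with order or position.

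**Cost.** Slightly more set-up per session and 2 degrees of freedom for test position; no extra visits or staff. If balancing was already done, a short statement of the method and the position term are enough.

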2.4.2 Primary Endpoint Analysis

The primary analysis focused on the subjective responses provided by participants during the acoustic task, comparing their experiences under different frequency response curves, hearing aid programs, and sound scenes. Scores for all 20 participants were tallied for the final analysis. Higher scores indicated a greater preference for a particular frequency response curve, while lower scores indicated a lesser preference. Additionally, the mean number of times participants preferred each frequency response curve (intervention) or rated the two interventions as equal in sound quality was calculated, based on the four sound quality attributes: comfort, noise intrusiveness, speech clarity (when applicable).

The analysis proceeded as follows:

1. **Chi-Square Analysis (First Step):** A chi-square test was conducted to compare the three means

(the mean number of times the standard curve was chosen, the mean number of times Variation #1 was chosen, and the mean number of times participants rated the sound quality as "same"). This test aimed to determine whether participants perceived a difference between the two curves by not selecting the "same" option.

2. **Chi-Square Analysis (Second Step):** Another chi-square test was conducted to compare the two means (the mean number of times the standard curve was chosen versus the mean number of times Variation #1 was chosen). This test assessed whether there was a preference between the two curves.

This process was repeated for each hearing aid program

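### In the primary acoustic task the raters were blinded but the investigator was not, and the plan describes no safeguard against cueing or against influence on how answers are recorded

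*Combined protocol and SAP*

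**What the plan says.** Section 2.1.1 makes two statements about blinding. The first concerns the acoustic task and masks the raters: "During the live preference ratings, participants were blinded to the program they were using". The same sentence then makes an exception for the person running the task: "although the investigator was aware of the program, as they programmed the hearing aids prior to testing". The second statement concerns the streaming task, where "both participants and investigators were blinded to the program being rated".

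Section 2.4.2 places the primary endpoint in the first of these tasks: "The primary analysis focused on the subjective responses provided by participants during the acoustic task". Its first chi-square step asks whether participants avoided the 'same' answer. Its second asks which curve they chose. Both steps are repeated for each hearing aid program.

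In the acoustic task the participant switches between curves on an iPhone. The answers are described only as tallied; who asked for them and who wrote them down is not stated. In the streaming task, "Responses were recorded on a laptop".

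For the US Matrix test, "Participants were asked to repeat sentences they heard while wearing hearing aids" carrying one of the two curves, or with no aids. A dB SNR score is then calculated for each condition. No section says who judged the repeated sentences, or whether that person knew which curve was in use.

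**The concern.** The endpoint most open to human influence has the weaker masking, and a secondary endpoint has the stronger. An investigator who knows which curve is the sponsor's proposal can affect a blinded rater without intending to: by tone, by suggesting another listen, by how a hesitant answer is followed up, or by how an ambiguous one is written down. The 'same' option widens the exposure, because a prompt to listen again can move answers off 'same' and so bear on the first test before direction is considered.

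At stake is whether a modest preference for Variation #1 can be read as the listeners' own. The reason given for the investigator's knowledge is that they programmed the aids. That explains why they know the two curves. It does not require them to know which slot holds which curve while ratings are taken.

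**Working it through.** The plan gives no figure on this point, so there is none to reproduce. The check sets the three tasks side by side and then gives a sense of scale.

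**Step 1. Masking and response capture, from sections 2.1.1, 2.4.2 and 2.4.3**

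| Task | Endpoint | Participant | Investigator | How answers are captured |
|---|---|---|---|---|
| Acoustic | Primary | Blinded | Aware of program | Tallied; recorder and method not stated |
| Streaming | Secondary | Blinded | Blinded | Laptop; who made the entries not stated |
| US Matrix | Secondary | Not stated (no-aid condition is evident) | Not stated | Sentences repeated; scorer not stated |

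**Step 2. Safeguards.** No section mentions coded slot labels, a tester separate from the fitter, scripted instructions, or direct entry of acoustic answers by the participant. Section 2.1.2 lists programming, real-ear measurement and the live ratings all at Visit 2, so nothing in the schedule separates fitting from rating.

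**Step 3. Sensitivity of a small preference count.** Assume one independent choice per participant, with n=20 (section 2.4.2) and 10 expected per curve. Chi-square is the sum of (observed − expected)²/expected.

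- 12 v 8: 2²/10 + 2²/10 = 0.8, p=0.37.
- 15 v 5: 5²/10 + 5²/10 = 5.0, p=0.025.

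The difference between these is 3 of 20 choices.

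**Step 4. Chance of a false finding for Variation #1.** Assume no true preference and an exact two-sided 5% sign test. The critical count c is the smallest with P(X ≥ c | n, 0.5) ≤ 0.025. This gives c=15 for n=20 (probability 0.0207) and c=18 for n=25, the upper end of section 2.2 (0.0216). If cueing moved the choice probability from 0.50 to p, the chance is P(X ≥ c | n, p):

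| p | n=20 | n=25 |
|---|---|---|
| 0.50 | 2.1% | 2.2% |
| 0.55 | 5.5% | 6.4% |
| 0.60 | 12.6% | 15.4% |
| 0.65 | 24.5% | 30.6% |

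**Step 5. What these figures are not.** The values of p are assumed. The planned analysis also differs from this model: section 2.4.2 tests mean counts by program, with a 'same' category in the first step, and not 20 single choices. Steps 3 and 4 therefore show only that a study of this size has little protection if answers shift. They do not estimate bias. No size is given for the Matrix test, because the number of scored words and the slope needed to convert them to dB are not in the documents.

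**The case against.** The strongest reply is that the participant is the outcome assessor in a preference task, and the participants were blinded. That stands. A reader might infer from the investigator's awareness that the primary endpoint was rated open-label; the same sentence of section 2.1.1 rules this out.

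A reader might also picture the investigator in the room, seeing which curve was active at each moment. The documents do not say so. They support knowledge of the assignment only, and the participant did the switching.

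Nor does the streaming task prove that live aids can be double-blinded. There, "Participants were asked to wear headphones while listening to three versions of the same pre-recorded stimulus", and how the masking was achieved is not described. The acoustic task used individually programmed aids, and real-ear measurement could reveal each curve to the fitter. This is a fair limit, and it means that any slot code must be assigned after measurement. It does not remove the point, since the only obstacle the plan states is that the investigator did the programming.

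On the Matrix test, a reader might infer unmasked scoring. The documents are silent, which is missing information and not a stated defect. The gap also matters mainly for one secondary comparison, standard v Variation #1.

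Finally, section 1.1 calls the study exploratory, much of the text is in the past tense, and the single blinding is openly disclosed. A redesign cannot change data already collected, so for those data the remedy is reporting.

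**Conclusion.** The point holds in a limited form, centred on the acoustic task. The raters were blinded. The investigator knew the program assignment, and no safeguard is described against cueing or against influence when answers are elicited and recorded. This leaves an avoidable, indirect risk of bias in a wholly subjective primary endpoint, in both the 'same' v different step and the direction-of-preference step.

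The size of the risk is unknown. The documents do not show that influence occurred, so it would be wrong to conclude that the preference result is biased. The move from 12 v 8 to 15 v 5 illustrates sensitivity under an assumed model of one choice per participant, and no more. The Matrix part comes down to a request to state who scored, and under what masking. The point is a worthwhile, cheap improvement and does not invalidate the design.

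**What to change.** In section 2.1.1:

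- **Coded slots.** After fitting and real-ear measurement are finished, have a script randomly assign the two curves to slots shown only as A and B. Keep the code unopened until that participant's ratings are complete.
- **Participant entry.** Have participants enter their own acoustic-task answers, including 'same', on the laptop already used for the streaming task.
- **Matrix test.** Use the same coded slots for the two aided conditions, keep the code closed until they are scored, and state who scores the sentences and under what masking. The unaided condition stays open.
- **Data already collected.** State who elicited and recorded the acoustic answers and who scored the Matrix test. Where the steps above were not used, report the unmasked investigator as a limitation on the preference conclusion.

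The cost is a script, reuse of the existing laptop and a few minutes of set-up per participant, with no added staff provided the code is assigned after measurement.
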